## 16.6 Sample Size

We aim to recruit 350 patients for this pilot study, which is a feasible sample at the study sites. With a sample size of 350, if the proportion of patients with a complete abortion is 95%, the 95% confidence interval of that proportion will be  $\pm 2.7\%$ . Abortion completion is an important clinical outcome.

We aim to survey all the pharmacists at the study sites, up to 50. This sample size will be determined by the number of pharmacists at the study sites. We have confirmed that there is at least one pharmacy at the site who is willing to dispense mifepristone, which is sufficient for the study. In the unlikely event that a willing and trained pharmacist is not on site to dispense the medication, the patient will be told when she can return to the pharmacy to have the prescription filled. Alternatively, the patient may return to the clinic, where the mifepristone will be dispensed. If that happens, the study will still cover the cost of the medication abortion, but the patient will be discontinued from the study.

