3.1 Patient arm

We will examine three outcomes related to patient participants' clinical experience and satisfaction with the pharmacist dispensing model. These will include two clinical outcomes: 1) effectiveness of medication abortion and 2) adverse events, as well as an outcome from the patient perspective: 3) satisfaction with the pharmacy experience at day 2. Effectiveness of medication abortion is defined as the proportion of participants who have a complete abortion with medications alone and do not undergo vacuum aspiration. Given the accuracy of patient self-assessment of abortion completion, we will use self-reported survey data to document

abortion outcome if the participant does not have follow-up contact with the clinic. Adverse events will be captured up to 6 weeks after participants are recruited into the study, and any ongoing adverse events will be followed until resolution. Adverse events are defined as serious using the FDA criteria and include death, hospitalization, blood transfusion, and surgery. Information about adverse events will be collected from abstracted data from patients' charts and self-reported data in patients' surveys. The satisfaction outcome will be based on participants' ratings on a Likert scale. On the day 2 survey, we ask participants "Overall, how satisfied were you with your experience at the pharmacy when you got the abortion pill?" with response options "Very satisfied," "Somewhat satisfied," "Somewhat dissatisfied," and "Very dissatisfied." We will dichotomize responses by those who report being very satisfied compared with all other responses. All demographic variables and pharmacy experience responses will be collected from patient surveys except gestational age at the clinic visit, which will come from clinical charts. Missing survey data for age, race and ethnicity, and parity will be obtained from patients' clinical chart data when available. We will conduct all analyses using Stata 15 and report significance at $P < .05$.

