series of multivariable logistic and linear regression analyses using Generalized Estimating Equation (GEE) models to assess whether study implementation is associated with pharmacists' overall medication abortion knowledge and on 15 individual medication abortion topics, ease and support of pharmacist dispensing of Mifeprex®. Coefficients in adjusted analyses examining overall medication abortion knowledge will represent the difference in mean knowledge scores between baseline and follow-up. We will conduct analyses in Stata 15.1 (StataCorp, College Station, TX).

We will also assess perceived benefits and challenges of pharmacist mifepristone dispensing. For perceived benefits, we will ask if this model “may improve access for women”, “expands pharmacists’ role in providing reproductive health services”, and “may streamline delivery of medications”, coding as dichotomous outcomes (yes/no). We will assess perceived ease of model implementation at baseline (anticipated ease) and follow-up (experienced ease) and personal support for pharmacist dispensing of mifepristone, measured on a four-point Likert scale, but coded dichotomously. We will code ease of implementation as very easy vs. somewhat easy/somewhat difficult/very difficult, and personal support for pharmacist dispensing of mifepristone as very supportive vs. somewhat supportive/somewhat unsupportive/very unsupportive.

For challenges, we will examine both anticipated (baseline) and experienced (follow-up) challenges (for example, lack of familiarity with medication or support from other pharmacists). At follow-up, we will assess how sufficient the medication abortion training and resources of the training were perceived to be (ranging from very sufficient to very insufficient), as well as satisfaction with pharmacy dispensing of mifepristone (ranging from very satisfied to very unsatisfied).

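### Top-box coding of the four-point ease and support ratings hides movement towards difficulty or opposition, and the Day 2 coding leaves patient dissatisfaction unreported

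*SAP*

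**What the plan says.** SAP 3.2 describes the ratings of ease and personal support as "measured on a four-point Likert scale, but coded dichotomously". The cut for ease is explicit: "We will code ease of implementation as very easy vs. somewhat easy/somewhat difficult/very difficult". Support is handled in the same way, with only the top answer set apart: "personal support for pharmacist dispensing of mifepristone as very supportive vs. somewhat supportive/somewhat unsupportive/very unsupportive". Ease is rated as anticipated at baseline and as experienced at follow-up. The same section names ease and support among the outcomes of the GEE models for the effect of study implementation, so each binary code feeds a before-after contrast.

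SAP 3.1 treats the Day 2 patient item, which has four response options, in the same way: "We will dichotomize responses by those who report being very satisfied compared with all other responses". This outcome is "satisfaction with the pharmacy experience at day 2", a single rating with no baseline and no comparator.

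No reason is given for any of these cuts. No ordinal analysis, alternative cut or four-category table is planned for these three items. Pharmacist satisfaction, a primary outcome in SAP 3.2, is described only by the ends of its scale, with no cut stated.

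The sample sizes are in Protocol 16.6: "We aim to survey all the pharmacists at the study sites, up to 50" and "We aim to recruit 350 patients for this pilot study". The synopsis row for number of subjects gives 300 patients.

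**The concern.** Protocol 16.3 lists ease of implementation among the variables that assess feasibility, which is the primary objective. A model that is hard to run would show as pharmacists rating it somewhat or very difficult. Under the SAP's coding those answers score the same as 'somewhat easy'. The planned contrast answers whether fewer pharmacists found dispensing very easy, not whether more found it difficult. Support has the same problem at its lower end.

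For patients the issue is narrower. The coded outcome gives the share who were very satisfied and leaves the rest undivided. If 80% are very satisfied, the share dissatisfied could be anything from 0% to 20% (100 − 80), and the named outcome would be the same.

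There is also a question of efficiency. Reducing four ordered levels to two discards information, and the pharmacist sample is small.

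**Working it through.** The plan gives no power, effect size or response distribution for these ratings, so it has no figure to reproduce. Its one sample-size calculation concerns complete abortion and does not bear on this point.

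**Inputs.** From the documents: the cuts (SAP 3.1 and 3.2), at most 50 pharmacists and 350 patients (Protocol 16.6), and alpha 0.05 (stated in SAP 3.1 only; two-sided assumed). Protocol 8.2 expects staff turnover, so the overlap between waves is partial and unknown; independent and paired waves are both shown. Assumed: all category distributions, the size of shift, and a latent correlation of 0.5 when paired. Simulations use 4,000 samples. Paired top box is tested by McNemar, which corresponds to a time-only logistic GEE, and the paired score by a paired t test.

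**Step 1: masking.** Order the categories from very easy (4) to very difficult (1). Let ease move from 40/40/15/5% to 40/10/30/20%.
- Share rating it difficult: 15 + 5 = 20% becomes 30 + 20 = 50%.
- Top box: 40% at both waves, odds ratio exactly 1.
- Mean score: 4(0.40) + 3(0.40) + 2(0.15) + 1(0.05) = 3.15 becomes 4(0.40) + 3(0.10) + 2(0.30) + 1(0.20) = 2.70, a fall of 0.45.
- Score variances: 10.65 − 3.15² = 0.7275 and 8.70 − 2.70² = 1.41. With 50 independent responses per wave, SE = √[(0.7275 + 1.41)/50] = 0.207, and power ≈ Φ(0.45/0.207 − 1.96) = Φ(0.22), about 58%.

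Simulated power, 50 per wave:

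| | Top box | 1-4 score | Easy vs difficult |
|---|---|---|---|
| Independent | 5% | 58% | 90% |
| Paired | 5% | 78% | 97% |

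A second example, 20/60/15/5% to 20/30/30/20% with 40 pairs, gives 4% for top box and 81% for the score. In both, the top-box test rejects at about its type I error rate.

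**Step 2: power under a uniform shift.** Here every cumulative odds is divided by 2.5 (worsening), so the top box moves too. For example, 40% has odds 0.667; 0.667/2.5 = 0.267, or 21%. Large-sample relative efficiency of top box to the full ordinal scale is p₁(1 − p₁) / [(1 − Σp³)/3]. For 20/40/30/10% this is 0.16 / [(1 − 0.100)/3] = 0.16/0.30 = 0.53.

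| Baseline distribution (%) | Relative efficiency | Independent, 50 per wave: top box vs score | Paired, 50: top box vs score |
|---|---|---|---|
| 20/40/30/10 | 0.53 | 34% vs 70% | 40% vs 91% |
| 30/40/20/10 | 0.70 | 46% vs 72% | 58% vs 91% |
| 40/40/15/5 | 0.83 | 53% vs 67% | 69% vs 90% |
| 60/30/7/3 | 0.95 | 65% vs 64% | 78% vs 84% |
| 80/15/3/2 | 0.99 | 53% vs 49% | 68% vs 66% |

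With 40 pairs the figures are 33% vs 76-84% at a 20% top-box share (depending on the split below it), 55% vs 81% at 40%, 67% vs 76% at 60% and 54% vs 56% at 80%.

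For an improvement of the same size (50 per wave, independent) the loss is smaller: 52% vs 69% at 20%, 64% vs 67% at 30%, and none from 40% up.

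The easy-versus-difficult split alone is not a good replacement. For the uniform worsening at a 60% top-box share it has 37% power, against 65% for top box (independent).

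**Step 3: patients.** With one rating there is no change to mask. The missing result would be estimated well. If 5% were dissatisfied (assumed), the Wald half-width is 1.96√(0.05 × 0.95/350) = 2.28 points, or 2.47 points with 300 patients.

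**The case against.** The case for leaving the plan alone has several parts.

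- **A strict criterion.** A prespecified top-box cut does not count lukewarm answers as success. That is a legitimate choice and a reason to keep the cut. It does not supply the share reporting difficulty.
- **The masking example is constructed.** It holds the top box exactly fixed, which a uniform shift would not do. This stands: the example shows what can happen, not what is likely. Under a uniform worsening the top box falls as well.
- **Ease and support are not named outcomes in the SAP.** Its pharmacist outcomes are objection, satisfaction and knowledge. This is true, but Protocol 16.3 places ease under feasibility.
- **Difficulty is captured elsewhere.** SAP 3.2 has challenge items and training sufficiency. The protocol has monthly checks on who stops dispensing (11.2), reasons for refusal (11.3), interviews, and patients' reasons for dissatisfaction (16.4). These offset the gap in part, but none gives the proportion rating implementation difficult, or its change.
- **Ordinal models are fragile here.** With 50 pharmacists a 5% category holds two or three people. This is a fair argument against making a cumulative-logit GEE the main analysis.

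Two stronger readings are tempting. A reader might infer that top-box coding always costs much power. The documents give no response distribution, and at a 60-80% top-box share the loss is small to nil. A reader might also extend the change and small-sample arguments to patient satisfaction. It is rated once in about 350 patients, so neither applies.

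**Conclusion.** The point holds for ease and support. Movement confined to the lower three categories does not register in the planned GEE; this follows from the coding and needs no assumption. How often such movement would occur cannot be judged from the documents.

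The power loss is conditional. For a worsening that divides the odds by 2.5, with 50 per wave, it is about 36 points (independent) to 51 points (paired) at a 20% top-box share and 14 to 21 points at 40%. At 60% it is at most about 6 points, and at 80% there is none. These figures rest on the assumed distributions, shift and correlation.

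For patient satisfaction the fault is one of reporting only: the level of dissatisfaction is not a named result. This is a cheap improvement, not a flaw that invalidates the plan.

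**What to change.** In SAP 3.2:
- Keep the top-box analysis of ease and support.
- Add a prespecified GEE on the 1-4 score for both items, comparing follow-up with baseline.
- Name the easy-versus-difficult and supportive-versus-unsupportive splits as sensitivity analyses.
- Tabulate all four categories at each wave.

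In SAP 3.1, report all four Day 2 satisfaction categories, with the proportion dissatisfied (somewhat plus very) and its 95% CI beside the proportion very satisfied.

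No new data are needed. The cost is a few table lines, an equal-spacing assumption for the score that needs a sentence of explanation, and one more contrast per item to interpret. Writing this in before the analysis also prevents a cut being chosen after the responses are seen.
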